9.3.5. Follow-up in the active surveillance population

Patients in the active surveillance population will be followed from index date until first occurrence of each outcome of interest, treatment switch or discontinuation, with the appropriate outcome-specific extension to exposure (i.e. 90 day window for acute events, and "once-exposed always at risk" approach for non-acute events like malignancy as described below), and with death, lost medical/pharmacy coverage, and end of data collection (30 June 2025) treated as censoring events.

Acute events of interest in this study are thought to potentially occur at a higher rate while on drug, but that increased risk subsides after the drug is discontinued (i.e., serious and opportunistic infections, herpes zoster reactivation, MACE, VTE, GI perforation, PML). These events will be evaluated over a risk window that includes time from drug initiation until 90 days after end of treatment. When a patient initiates a new therapy within the 90-day

[figure not shown]
extension, the time and events during the overlapping period will be assigned to both treatments. An example of the as-treated approach with the 90-day extension period is provided in the scenario illustrated below.

------ represents risk period counted
+++++ represents time not included in the risk period
x represents occurrence of an acute safety event of interest such as MACE
) represents drug discontinuation
| represents tofacitinib initiation
| represents biologic initiation
| represents 90-day extension period

In the above scenario, the patient has two biologic initiations and a tofacitinib initiation. The initiation of tofacitinib therapy occurs within the 90-day extension period for the first biologic. Thus, the time and event during the overlapping period will be assigned to both the first biologic and tofacitinib. Specifically, for the first biologic initiation, a safety event occurred within the 90-day extension period, and exposure time is counted from the time of drug initiation (Index date 1) until the occurrence of the safety event. For the tofacitinib initiation, one safety event occurred and exposure time is counted from Index date 2 (date of initiation of tofacitinib which occurs within the 90-day extension period of the first biologic initiation) to the occurrence of the safety event (which also occurred within the 90-day extension period for the first biologic). Tofacitinib treatment was discontinued when the safety event occurred, and there is a period of time where no treatment is used. For the second biologic initiation, one safety event occurred and exposure time is counted from Index date 3 to the safety event.

For the purpose of analysis, the patient has 2 biologic initiations and a tofacitinib initiation:

A sensitivity analysis whereby if a new medication is started during the 90-day window after discontinuation of a previous medication, initiation of the new medication will stop the 90-day risk window, and any event prior to the new medication start will be assigned to the discontinued medication will also be conducted and further discussed in the SAP. The 90-day extension period is implemented in part to accommodate ongoing exposure to treatments with longer half-lives, and in part to ensure that any subclinical or undiagnosed illness at time of end of treatment is captured. For each patient, follow-up time contributing to one of the three treated cohorts will be calculated as the sum of dispensed medication days (based on days supply) plus the 90-day extension period.

For NMSC and malignancies, surgery for UC, and death (and as a sensitivity analysis for PML), the occurrences of which are expected to be delayed relative to the time of exposure, the outcomes will be evaluated from drug initiation until the first event or loss to follow up, reflecting a "once-exposed always at risk" paradigm. If a patient switches to a new drug, the subsequent observation time will contribute to multiple therapies.

Additionally, for patients experiencing a specific event of interest (except death), follow-up will be censored for that particular event; however follow-up will continue for all other events of interest.

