Patients may switch between the tofacitinib and contextualization cohorts over time if inclusion/exclusion criteria listed below are met. Additionally, patients will be eligible for entry into a particular cohort each time they start a new therapy within the same drug class. For acute endpoints, patients will be censored from a particular cohort when they start a new therapy in a different drug class. For the endpoint of MACE, for example, patients in Cohort 1 (UC patients initiating treatment with tofacitinib) will be censored if and when they switch to a specific biologic agent, but will be eligible for subsequent inclusion into Cohort 2 (patients initiating treatment with biologics). For non-acute outcomes such as malignancy and death, outcomes will be evaluated using a "once exposed always at risk" paradigm (as described in Section 9.3.5).

Formal definitions of index dates/start of follow-up are provided in Sections 9.3.4.2 and 9.3.5.Details of exposure measurement (e.g., allowing specified gaps between prescriptions in continuous exposure, etc.) will be detailed in the statistical analysis plan (SAP).

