9.7.2. Analysis of safety endpoints of interest

For the safety endpoints of interest, descriptive statistics, counts and proportions, cumulative incidence proportions, and crude incidence rates (i.e., number of events per person-years) and associated two-sided 95% confidence intervals will be calculated as appropriate. UC patients with a baseline history of an outcome of interest will be excluded from the calculation of the incidence rate for that particular outcome of interest (e.g. patients with a baseline history of malignancy will be excluded from the calculation of the incidence rate for malignancy).

Several subgroup analyses will be performed. These include (but are not limited to) stratification by:

- Tofacitinib dose (5 mg twice daily vs. 11 mg once daily vs. 10 mg twice daily vs. 22 mg once daily)
- Patient characteristics such as age at index date, including a subgroup analysis of patients <50 years vs. ≥50 years, and patients <65 years vs. ≥65 years
- For the outcomes of VTE and MACE, subgroup analysis of patients with ≥1 thrombosis risk factors (as defined in Section 9.3.1.1) vs. no thrombosis risk factors, and
- Key indicators of disease severity such as number of previous biologic treatments (i.e. prior biologic use vs. none; among those with prior biologic use, 1st biologic vs. 2nd biologic vs. ≥3 biologics)

This will be a time to first event analysis based on an index date defined for each cohort with appropriate censoring rules applied (based on therapy switches, end of study, etc.) for those

who do not experience an event by end of follow-up period. Rates will be expressed as the number of events/100 person-years of follow-up.

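### Section 9.3.5 gives two incompatible rules for acute-event person-time in Cohorts 1–3: calendar time at risk, and summed days' supply plus 90 days

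*Protocol*

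**What the plan says.** Section 9.3.5 describes follow-up for acute events in three places.

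- **General rule.** Patients are "followed from index date until first occurrence of each outcome of interest, treatment switch or discontinuation, with the appropriate outcome-specific extension to exposure". Death, loss of coverage and 30 June 2025 are censoring events. For acute events: "These events will be evaluated over a risk window that includes time from drug initiation until 90 days after end of treatment". This is a calendar interval.
- **Worked example.** For the first biologic, "exposure time is counted from the time of drug initiation (Index date 1) until the occurrence of the safety event". The tofacitinib course and the second biologic are also counted from their index dates to the event. This too is calendar time.
- **Calculation sentence.** After the example, the section says that "follow-up time contributing to one of the three treated cohorts will be calculated as the sum of dispensed medication days (based on days supply"; a further 90 days are then added. This is a total of supply, not an interval.

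Section 9.2.1.2 leaves exposure measurement to the SAP and gives "allowing specified gaps between prescriptions in continuous exposure" as an example of what the SAP will specify. No gap length is stated.

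For NMSC, malignancies, surgery for UC and death, Section 9.3.5 uses a different window: "the outcomes will be evaluated from drug initiation until the first event or loss to follow up, reflecting a 'once-exposed always at risk' paradigm". Days' supply plays no part there. Section 9.7.2 gives the scale: "Rates will be expressed as the number of events/100 person-years of follow-up".

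**The concern.** An incidence rate is valid only if events and person-time are taken over the same days. Under the general rule, an acute event on any day between initiation and 90 days after end of treatment counts. Under the calculation sentence, the denominator contains only days covered by dispensed supply, plus 90. A day inside a bridged refill gap can therefore yield an event and yet contribute no person-time. Where fills overlap and the surplus is not carried forward, the same calendar day is counted twice.

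At stake are the rates that Section 9.3.5 names as acute: serious and opportunistic infections, herpes zoster reactivation, MACE, VTE, GI perforation and PML, in the tofacitinib, biologics and immunomodulator cohorts. Crude rates per 100 person-years are the main safety output. A programmer following the calculation sentence and one following the worked example would report different rates from the same data.

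**Working it through.** **The plan's own figure.** The protocol states no rate or person-time total, so there is nothing to reproduce. The check compares the two denominators.

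**Inputs from the protocol (Section 9.3.5).** The extension is 90 days. Events are counted from initiation to end of treatment plus 90 days.

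**Assumed inputs, not in the protocol.** Treatment span of 365 days; share of those days covered by supply (coverage) of 70% to 105%; all gaps bridged; surplus supply not carried forward.

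**Formulas.**
- Calendar time = span + 90
- Supply time = coverage × span + 90
- Factor = calendar time / supply time. This is how far a rate with the supply denominator departs from the rate per day at risk.

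| Coverage (assumed) | Calendar days | Supply days | Factor | Rate |
|---|---|---|---|---|
| 100%, no gaps | 455 | 365 + 90 = 455 | 1.00 | no difference |
| 90% | 455 | 328.5 + 90 = 418.5 | 1.087 | 9% too high |
| 80% | 455 | 292 + 90 = 382 | 1.191 | 19% too high |
| 70% | 455 | 255.5 + 90 = 345.5 | 1.317 | 32% too high |
| 105%, oversupply | 455 | 383.25 + 90 = 473.25 | 0.961 | 4% too low |

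**The same check by refill gap.** Take 12 fills of 30 days (assumed). Supply time is 12 × 30 + 90 = 450 days. Calendar time is 450 + 11 × gap.
- Gap 0: 450 days, factor 1.00
- Gap 5 days: 505 days, factor 505/450 = 1.12
- Gap 10 days: 560 days, factor 560/450 = 1.24
- Refills 3 days early: 417 days, factor 417/450 = 0.93

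**On the rate scale.** A simulation with a constant rate of 3 per 100 person-years (assumed), a 365-day span and 80% coverage gave about 3.0 with calendar time and about 3.6 with supply time. This agrees with 3 × 1.191 = 3.57.

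**Scope.** The calculation sentence names the three treated cohorts, so Cohort 4 is outside it. It adds the 90-day extension, which belongs to acute events only. Malignancies, NMSC, surgery for UC and death run from initiation to first event or loss to follow-up, so the primary objective does not use it.

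**The case against.** The strongest reply is that the sound rule is already in the same section. The general rule and the worked example both use calendar time, and the calculation sentence could be loose shorthand. Exposure measurement is expressly left to the SAP, which could settle the matter. Much of this stands: the protocol contradicts itself and has not settled on a wrong denominator. It does not follow that the SAP can resolve it silently. The sentence says how follow-up time will be calculated, so an SAP following either rule departs from the other. Any permitted gap above zero alters the size of the mismatch without removing it.

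A reader might draw four stronger conclusions, which the protocol does not support.

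- **That the formula adds the full 90 days with no cut at the event or at censoring.** The sentence does not repeat the cuts, but Section 9.3.5 names the censoring events and ends follow-up for an outcome once it occurs, its example stops at the event, and Section 9.7.2 specifies time to first event with censoring.
- **That gap bridging is a fixed rule.** Section 9.2.1.2 offers it only as an example for the SAP. How early refills are treated is not stated; if surplus supply is carried forward to date the end of treatment, the overlap effect disappears.
- **That all the study's rates are affected.** The primary endpoint is not.
- **That contrasts between cohorts are biased by differing refill patterns.** This is possible, but the protocol gives no refill data by drug, specifies no hypotheses, and uses the other cohorts for context.

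**Conclusion.** The point holds as an internal contradiction. Section 9.3.5 defines acute-event person-time for Cohorts 1–3 both as calendar time at risk and as summed supply plus 90 days, and only the calendar rule matches the window in which events are counted.

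The size depends entirely on refill behaviour, which the protocol does not describe. For a 365-day course with bridged gaps, the supply rule makes rates about 9% to 32% too high as assumed coverage falls from 90% to 70%. It makes them about 4% too low with 5% oversupply that is not carried forward, and leaves them unchanged with gap-free supply. The direction therefore cannot be fixed in advance. Malignancy excluding NMSC, NMSC, surgery for UC, death and Cohort 4 are untouched.

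**What to change.** Replace the calculation sentence in Section 9.3.5 with one rule, for example:

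*For acute events in Cohorts 1–3, person-time is the number of calendar days from index date to the earliest of first event, death, loss of medical or pharmacy coverage, 30 June 2025, or end of treatment (by discontinuation or switch) plus 90 days. Bridged gap days are included and overlapping supply is counted once. Days' supply is used only to date the end of treatment.*

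The permitted gap, and whether surplus supply is carried forward when dating the end of treatment, can stay in the SAP. The sensitivity analysis that stops the window at a new initiation stays as stated. The sentence in Section 9.2.1.2 on censoring acute endpoints at a change of drug class should refer to this rule, so that a switch is handled the same way in both places.

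The cost is a one-sentence edit and the matching program rule. Both planned interim report dates (30 June 2022 and 30 June 2024) precede this protocol version, so the sponsor should also state which rule any interim acute-event rates used. Otherwise a change in rates between the interim and final reports could reflect the denominator alone.

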9.3.6. Endpoints of Interest

To assess tofacitinib utilization patterns, the main endpoint of interest to be captured in the interim and final study reports will be the indication for tofacitinib use, classified as on-label, off-label, or unknown, based on medical events (diagnoses and/or medication use) identifiable around the time of the first ever tofacitinib prescription. The date of first prescription of tofacitinib during the study period is the index date as described in Section 9.3.4.1. All patients' tofacitinib use will be classified as on-label indication, off-label indication or unknown indication according to the first prescription of tofacitinib received, regardless of later prescriptions. The on-label, off-label and unknown indication classifications will be made based on the authorized indication(s) as of the index date.

For the active surveillance portion of the study, the safety events of interest (to be defined via ICD-code based algorithms in the SAP) which will also be captured in the interim and final study reports include the following:

- Malignancy, excluding NMSC
- Lung cancer
- Lymphoma
- NMSC
 - Serious infections
 - Opportunistic infections (e.g. tuberculosis)
 - HZ reactivation

- MACE
- VTE (DVT and PE)
- Myocardial Infarction (MI)
- Hepatic events
- PML (PML)
- GI perforations
- ILD
- Fractures
- Surgery for UC (e.g. colectomies, partial colectomies, and proctocolectomies; full list of procedures to be detailed in SAP)
- Death

Of note, due to limitations related to the Marketscan database, only in-hospital deaths can be captured (outcome will be defined via an algorithm currently under development, details of which will be outlined in the SAP). Deaths occurring in other environments such as home, non-hospital institutions, etc., cannot be captured.

The above list of safety endpoints may be extended with additional sub-diagnoses or new health-related outcomes as agreed to by study researchers and Sponsor before the interim reports and final study report. These decisions will be made prior to initiation of analyses and documented in the SAP kept on file by the Sponsor.

In addition, the final study report will include the number of tofacitinib-exposed pregnancies.

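### In-hospital death is assigned solely to the once-exposed-always-at-risk window as a delayed outcome; that reason fits cancer deaths but not in-hospital deaths from the acute events the protocol ties to being on drug

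*Protocol*

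**What the plan says.** Two places in the protocol set the window for death. Section 9.2.1.2 classes it as non-acute: "For non-acute outcomes such as malignancy and death, outcomes will be evaluated using a" once-exposed-always-at-risk rule. Section 9.3.5 gives the reason, a lag behind exposure ("For NMSC and malignancies, surgery for UC, and death (and as a sensitivity analysis for PML), the occurrences of which are expected to be delayed"), and the window: "the outcomes will be evaluated from drug initiation until the first event or loss to follow up". On switching it adds: "If a patient switches to a new drug, the subsequent observation time will contribute to multiple therapies".

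The same section treats another group of outcomes differently, on the premise that their raised risk ends once treatment stops: "Acute events of interest in this study are thought to potentially occur at a higher rate while on drug, but that increased risk subsides after". That group comprises "serious and opportunistic infections, herpes zoster reactivation, MACE, VTE, GI perforation, PML". For them, "These events will be evaluated over a risk window that includes time from drug initiation until 90 days after end of treatment". PML is placed in this group and also receives the once-exposed window as a sensitivity analysis.

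Section 9.3.6 states that, because of the database, "only in-hospital deaths can be captured". Section 9.7.3 says the interim reports will carry rates both on drug and ever since treatment start, without naming the outcomes to which each applies. Section 9.7.4, on the final report, names no risk window for any outcome.

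**The concern.** The protocol gives one reason for the long window, expected delay. That is reasonable for death from cancer. It is not reasonable for death during an admission for sepsis, a cardiovascular event, pulmonary embolism or perforation, if the protocol is right that the raised risk of such events subsides after stopping. The captured deaths are all in hospital, so deaths during admissions of that kind are among those the study can see.

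What is at stake is how the death row can be read. Under the stated rule, a death long after tofacitinib was stopped, while on another drug, counts for tofacitinib. A death on tofacitinib also counts for an earlier biologic or immunomodulator started since 30 May 2018. The first dilutes an on-treatment excess within Cohort 1. The second passes part of it to the cohorts meant to give context.

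**Working it through.** **1. What can be reproduced.** The protocol gives no treatment duration, mean follow-up, expected number of deaths or rate ratio, so it has no figure to reproduce. It fixes only the calendar limit: 30 May 2018 to 30 June 2025 is 2,588 days, and 2,588/365.25 = 7.09 years at most.

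**2. The two rules side by side (sections 9.2.1.2 and 9.3.5).**

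| Outcome | Stated timing of risk | Window |
|---|---|---|
| Serious and opportunistic infections, HZ, MACE, VTE, GI perforation | Higher on drug, subsides after stopping | Initiation to 90 days after end of treatment |
| PML | As above | As above, plus once-exposed as sensitivity analysis |
| Malignancy, NMSC, UC surgery | Delayed | Once-exposed only |
| Death | Delayed | Once-exposed only |

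Death mixes causes from the first and third rows but takes the window of the third. The one sensitivity analysis specified for the 90-day window concerns a new drug started within it and does not reach death.

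**3. Attenuation within a cohort (illustration).** Let f be the share of follow-up inside the on-drug window, f = (years on drug + 90/365.25) / years followed. If the on-treatment ratio is R, the ratio outside the window is 1 and the background rate is constant, the ratio seen under the once-exposed rule is 1 + f(R − 1). Example: one year on drug and five followed gives f = (1 + 0.246)/5 = 0.249. With R = 2 the ratio seen is 1 + 0.249 × 1 = 1.25.

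| Years on drug (assumed) | Years followed (assumed) | f | R = 1.5 seen as | R = 2 seen as | R = 3 seen as |
|---|---|---|---|---|---|
| 0.5 | 7.09 | 0.105 | 1.05 | 1.11 | 1.21 |
| 0.5 | 3 | 0.249 | 1.12 | 1.25 | 1.50 |
| 1 | 5 | 0.249 | 1.12 | 1.25 | 1.50 |
| 1 | 3 | 0.415 | 1.21 | 1.42 | 1.83 |
| 2 | 5 | 0.449 | 1.22 | 1.45 | 1.90 |
| 2 | 3 | 0.749 | 1.37 | 1.75 | 2.50 |

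**4. Sharing between cohorts.** Take a patient who starts a biologic, switches to tofacitinib and dies in hospital on tofacitinib a year later. Under the once-exposed rule the death counts in Cohorts 1 and 2. Under treatment plus 90 days it counts in Cohort 1, and in Cohort 2 only if it falls within 90 days of the end of the biologic. This blurring comes on top of step 3 and is not in the table.

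**5. What the shorter window costs in precision.** Assume 2,000 initiators, a background of 0.3 in-hospital deaths per 100 person-years, R = 2, one year on drug and five followed.
- Treatment plus 90 days: 2,000 × 1.246 × 0.003 × 2 = 15.0 deaths, ratio 2.0. The 95% limits on the rate are roughly a factor exp(1.96/√15) = 1.66 either way.
- Once-exposed: 15.0 + 2,000 × (5 − 1.246) × 0.003 = 37.5 deaths. Background over five years is 2,000 × 5 × 0.003 = 30, so the ratio is 37.5/30 = 1.25. The limits are roughly a factor exp(1.96/√37.5) = 1.38 either way.

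In this example the shorter window has fewer deaths and wider limits, yet separates better from background: ln 2 × √15.0 = 2.7 against ln 1.25 × √37.5 = 1.4.

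**The case against.** The once-exposed window is defensible for death. The endpoint includes cancer deaths, and stopping follow-up 90 days after treatment can lose deaths in patients taken off drug because they were deteriorating. That stands, and it is why the present analysis should stay. A reader might infer that the window is wrong for death and should be replaced; the documents do not support that.

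A reader might also infer that no on-drug death rate will ever be reported. Section 9.7.3 promises on-drug interim rates, and section 9.3.6 lists death among the events in the interim reports, so the text may be meant to cover death. It names no outcomes, however, and if it does include death it departs from section 9.3.5. The silence of section 9.7.4 proves little, since it is silent for MACE and VTE too.

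Nor do acute harms go unexamined. Infections, MACE, VTE, GI perforation and PML all have the treatment-plus-90-day window, so an excess in those events would be sought there. What is left uncovered is narrower: differences in case fatality, and on-drug deaths from causes not listed.

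Finally, section 9.7 lets the SAP modify the plan, and the SAP, which is not at hand, may add a second window. But the protocol itself fixes both the window and its rationale, and section 9.3.5 would still need to agree with any addition. The comparison with PML is only partial, since PML starts as an acute event; it shows that two windows for one outcome are already accepted here, not that death is singled out.

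**Conclusion.** The point holds as a matter of rationale and interpretability. The stated reason for the window does not fit part of the endpoint, and following the rule attenuates any on-treatment difference in in-hospital death and spreads deaths across therapies. The direction requires an excess confined to treatment plus 90 days and material follow-up outside it. Section 9.9 accepts the same mechanism on a smaller scale when it warns that the 90-day extension may understate rates for drugs with a shorter half-life.

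The figures above are illustrative only: time on drug, follow-up, background rate and on-treatment ratio are all assumed. It would be tempting to read them as the expected bias, but the protocol contains nothing from which that could be derived. It plans crude rates with confidence intervals, with no hypotheses and no stated rate ratios, so the harm would lie in an informal comparison of cohorts.

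Death is secondary, descriptive and, by section 9.9, incompletely captured through an algorithm that will not be validated. The primary malignancy endpoint is unaffected. This is a question of analysis window, not of clinical management. The change is worth making because it is cheap.

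**What to change.** - **Section 9.3.5:** keep the once-exposed death rate. Add, as a supplementary analysis for Cohorts 1 to 3, the in-hospital death rate from initiation to 90 days after end of treatment, under the overlap rule already set for acute events. Limit the statement about expected delay to malignancy, NMSC and UC surgery, and say that death is reported over both windows because it mixes acute and delayed causes.
- **Section 9.2.1.2:** align the sentence that classes death with malignancy as non-acute.
- **Section 9.7.3:** state which outcomes the on-drug and ever-since-start rates cover, consistently with section 9.3.5.
- **Section 9.7.4:** name both death rates for the final report.

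**Cost:** a few sentences and one more row per treated cohort, from windows already built for the acute events. Two downsides should be stated with the result. The shorter window has fewer deaths and wider intervals. Censoring may also be informative when treatment stops because the patient is deteriorating. For that reason the two rates should be shown together and neither should replace the other.
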